Nicotine Dependence and Smoking Cessation. Tobacco use is the leading cause of preventable disease and death in the United States. Critically, the majority of smokers (70%) express a desire to quit smoking, but the vast minority of quit attempts (<5%) are successful long-term (> 3 months). Recent theories have proposed that failed quit attempts could in part be due to reward dysregulation in the brain that occurs with chronic drug use. Over time, repeated exposure to drugs of abuse increases subsequent reward responses to drugs and drug cues. Simultaneously, responses to non-drug rewards diminish, eventually failing to motivate behavior. This imbalance in drug versus non-drug reward responses may motivate the choice of drug stimuli over non-drug stimuli. If individuals can learn to increase the reward response to personalized, non-drug cues, it could motivate their future behavior towards non-drug stimuli. Likewise, by balancing out the reward responses to drug and non-drug cues, this may reduce the frequency and need for drug interactions, resulting in improved smoking cessation outcomes. The proposed personalized study in nicotine-dependent individuals has the potential to dramatically improve health outcomes and reduce health care cost nationwide. If successful, this protocol could readily be adapted for application to a variety of addictive disorders that act on the DA system including cocaine and other stimulants.

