Research on self-activation of the DA system is highly relevant to mental health. Several neurologic and psychiatric disorders are affiliated with abnormalities in the dopaminergic system, including addiction, depression, schizophrenia, and PD2-9. The predominant treatments for these disorders include pharmacotherapy and psychotherapy. However, a current barrier to progress in the field is that for many diseases neither treatment completely cures the disorder nor alleviates the symptoms. Furthermore, pharmacotherapy is associated with adverse side effects while psychotherapy is effortful, time intensive, costly, and - perhaps most challengingly - produces effects that are not immediately apparent. Therefore patients must persist for long periods of time (e.g., days to months) without any direct indication of progress. The NIMH Strategic Research Plan demands novel interventions that are personalized, safe, effective, and efficient. This research proposal investigates the development of cognitive neurostimulation of the dopaminergic midbrain as a personalized, safe, effective, and efficient micro-intervention for nicotine-dependent individuals.

The proposed studies address fundamental unsolved problems in behavioral science and systems neurobiology. Understanding if and how rt-fMRI and/or rt-EEG neurofeedback can enable individuals with and without nicotine dependence to activate the reward-related regions will advance clinical practice by offering a novel micro-intervention for patients with dysfunctional dopaminergic systems across disease etiologies.

Design & Procedures

We will enroll up to 150 adults between 18-45 years. We will recruit up to 100 adults with nicotine dependence and 50 adults without nicotine dependence. We may need to screen additional participants in order to achieve 150 completed participants (we estimate screening 250 participants).

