Genetic measures: Saliva may be collected. If so, we will use a commercially available kit from Oragene (<http://www.dnagenotek.com/ROW/products/OG500.html>). This is a very simple procedure in which participants deposit saliva into a plastic tub. It is non-invasive and takes a few minutes. The tubes will be de-identified and labeled by participant ID number. They will be stored in a locked cabinet inside secure office space. These saliva samples are stable stored at room temperature and can be kept in room temperature storage for up to 5 years. Once data collection is complete, we will send them to the Duke University DNA Analysis Facility for one time analysis. We will examine genetic markers related to dopamine function. Examples include both SNPs (e.g., DRD1, DRD2) and VNTRs (e.g., DAT, MAOA).

Follow-up Phone Call/Debriefing:

For ND individuals: participants may be called and/or sent a link to a REDCap survey 1 day, 1 week, and/or 1 month following the MRI visit to assess if there is any change in their smoking behavior following study participation. We will ask participants if they have modified their smoking behavior in any way (e.g., # of cigarettes smoked, craving, etc, see Contemplation ladder and rtNic.01 Follow up Questionnaire as examples). During the last phone call, we will debrief participants regarding which group they were in (Veridical Feedback Group or Noise Control Group) and answer any remaining questions they have about the study.

Selection of Subjects

List inclusion/exclusion criteria and how subjects will be identified.

Inclusion Criteria:

18-55 years of age

In good general health

Male or Female

For ND individuals: Self-reported smoking \geq 5 combustible cigarettes per day

For ND individuals: Afternoon expired CO concentration of \geq 8 ppm

For ND individuals: Is willing and able to abstain from smoking for a few hours

Exclusion Criteria:

Current chronic/significant medical condition

Current or past 6 month use of prescription medications for psychiatric conditions (e.g., depression, anxiety)

Current or past 6 month diagnosis of anxiety, bipolar disorder, depression, OCD, schizophrenia, psychosis, or personality disorder.

Current substance abuse or dependence or history within the last 6 months (other than nicotine for ND individuals)

For ND individuals: Currently on nicotine replacement therapy

For ND individuals: Individuals who role their own cigarettes

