For MRI subjects: Positive drug test for anything other than marijuana

For MRI subjects: Daily cannabis use

For MRI subjects: Consume more than 21 alcoholic drinks per week

For MRI subjects: Use harder drugs (e.g., cocaine, methamphetamine) more than 10 times per year

For MRI subjects: Currently taking medication that directly acts on the dopamine system (e.g., L-DOPA).

We will record a list of all medications they are currently on and assess if they affect the dopamine system. If so, they will be excluded.

For MRI subjects: Claustrophobia or other contraindications to MRI scanning

For MRI subjects: If female, pregnancy as determined by urine pregnancy test on the day of MRI scanning

For MRI subjects: Presence of any metal in the body (e.g., implant, non-removable piercing, metal IUD)

For MRI subjects: Head injury resulting in loss of consciousness

For MRI subjects: Worked with metal (e.g., welding) or had an injury to the eye involving metal

For MRI subjects: If they weigh more than 200 pounds, the PIs will make their best judgement based on other factors including participant height and prior experience in with MRI scans

Inability to understand written and/or spoken English language

Any other participant characteristic, history, and/or behavior that in the opinion of the investigator would contraindicate participation in the study.

Subject Recruitment and Compensation

Describe recruitment procedures, including who will introduce the study to potential subjects. Describe how you will ensure that subject selection is equitable and all relevant demographic groups have access to study participation (per 45 CFR 46.111(a) (3)). Include information about approximately how many DUHS subjects will be recruited. If subjects are to be compensated, provide specific prorated amounts to be provided for expenses such as travel and/or lost wages, and/or for inducement to participate.

Research participants will be recruited from the Duke University community and surrounding Durham area via flyers posted in public places, print advertisements in local publications, advertisements online (e.g., Facebook, Reddit, Craigslist, DukeList) and word of mouth. To qualify for the study, participants who smoke must self-report smoking greater than or equal to 5 cigarettes per day, but otherwise be in

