To evaluate whether rt-fMRI neurofeedback improves the ability to increase reward-related brain activation in individuals with and without ND. To address this question we will compare individual's BOLD response to: baseline (passive viewing of reward images), Pre-Test (view personalized and non-personalized non-drug cues prior to neurofeedback), Training (view personalized, non-drug cues while receiving neurofeedback), and Post-Test (view personalized and non-personalized non-drug cues following neurofeedback). In this manner we will characterize and quantify individual's ability to increase brain activity to personalized, non-drug rewarding stimuli.

To examine the relationship between activation of reward-related regions via neurofeedback and dopamine availability (as assessed genetically). To assess this question we will first send the genetic data to the Duke University DNA Analysis Facility for analysis. Once the SNPs and VNTRs have been analyzed we will correlate individual's level of dopaminergic related genetic material (e.g., COMT, DAT) to their ability to regulate reward-related activation during the task.

To examine the effects of neurofeedback on clinically relevant outcomes, including reward responsivity and smoking related behaviors. To assess this we will examine participants brain activity during the Passive Viewing Task and the ReAcT. We will also perform a simple Delay to Smoking Assessment where we will measure (in minutes) how long participants take to smoke their first cigarette. We will also measure how many cigarettes they smoke during their break. We will correlate individual's ability to increase brain activation to personalized, non-drug cues in the ReAcT with both their time to initiate smoking and the number of cigarettes smoked.

Data & Safety Monitoring

Summarize safety concerns, and describe the methods to monitor research subjects and their data to ensure their safety, including who will monitor the data, and the frequency of such monitoring. If a data monitoring committee will be used, describe its operation, including stopping rules and frequency of review, and if it is independent of the sponsor (per 45 CFR 46.111(a) (6)).

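### Aim 3 correlates genotype with regulation ability and names no covariate or genotype coding, so population structure can appear as a dopamine-gene effect

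*Combined protocol and SAP*

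**What the plan says.** The third stated purpose, repeated under Data Analysis & Statistical Considerations, is "To examine the relationship between activation of reward-related regions via neurofeedback and dopamine availability (as assessed genetically"). The method is one sentence in that section: after laboratory analysis of the SNPs and VNTRs, the team will correlate each individual's "level of dopaminergic related genetic material (e.g., COMT, DAT) to their ability to regulate reward-related activation during the task". No coefficient, model, covariate, stratum or genotype coding is given there or elsewhere. The lead-in to the primary analyses says they run within and between subjects, but names no adjustment variable.

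Other sections describe who enters this correlation:

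- **Markers** (Genetic measures): "Examples include both SNPs (e.g., DRD1, DRD2) and VNTRs (e.g., DAT, MAOA"). With COMT from the analysis section, five markers are named, all as examples. Saliva collection is optional.
- **ND status** (Design & Procedures): "We will recruit up to 100 adults with nicotine dependence and 50 adults without nicotine dependence".
- **Sex** (Inclusion Criteria): "Male or Female". No proportion is given.
- **Ancestry** (Subject Recruitment and Compensation): "Research participants will be recruited from the Duke University community and surrounding Durham area". No restriction on ancestry, and no collection of or adjustment for it, is stated.

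**The concern.** Randomisation in this study assigns feedback, not genotype, so the gene comparison is observational. If a marker's allele frequency differs between ancestry groups, and those groups also differ in regulation score for any other reason, a correlation pooled over everyone is non-zero even when the gene does nothing. The same logic applies to any other factor linked to both genotype and outcome.

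Two further factors deserve a look. The background suggests that "failed quit attempts could in part be due to reward dysregulation in the brain that occurs with chronic drug use", which makes ND status a plausible correlate of the outcome. MAOA lies on the X chromosome, so men carry one copy and women two. Depending on coding, a single allele count across both sexes can carry sex with it.

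What is at stake is the reading of Aim 3. A significant result would be presented as evidence about dopamine availability, and nothing in the stated analysis would separate that from population structure.

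**Working it through.** The documents give no alpha, power, effect size or expected correlation for Aim 3, so there is no figure of theirs to reproduce.

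**From the documents:** at most 100 ND + 50 non-ND = 150 participants; both sexes; open recruitment.

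**Assumed:** two-sided alpha 0.05; no true gene effect; all 150 genotyped with one common outcome; equal ancestry groups and equal sexes; the allele frequencies shown; a gap of d SD in regulation score between groups.

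**Formulas, two equal groups**

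- Genotype with group: c_g = √[B/(B+W)], where B = (2Δp)²/4 and W is the mean of 2p(1−p) over the groups.
- Outcome with group: c_y = (d/2)/√(1+d²/4). This is 0.148 at d = 0.3 and 0.243 at d = 0.5.
- Spurious correlation: r = c_g × c_y.
- Rejection rate: Fisher's z of r times √(N−3), compared with ±1.96.

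**Ancestry, N = 150**

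- Frequencies 0.3 vs 0.4: B = 0.01, W = 0.45, c_g = √(0.01/0.46) = 0.147. Then r = 0.022 and 0.036, and the rates are 5.8% and 7.2%.
- Frequencies 0.2 vs 0.5: B = 0.09, W = 0.41, c_g = √(0.09/0.50) = 0.424. Then r = 0.424 × 0.148 = 0.063 and 0.424 × 0.243 = 0.103, and the rates are 11.9% and 24.0%.

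A simulation of 5,000 replicates per scenario agrees: 5.7% and 7.3% for the first pair, 12.3% and 24.1% for the second.

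**Ancestry, N = 75.** The same formula gives 5.4% and 6.1% for the first pair, and 8.3% and 14% for the second.

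**ND mix, 50 vs 100, N = 150 (simulated, at d = 0.3, 0.5 and 0.8)**

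| Allele frequency, non-ND vs ND | 0.3 SD | 0.5 SD | 0.8 SD |
|---|---|---|---|
| 0.30 vs 0.35 | 5.4% | 5.1% | 6.2% |
| 0.30 vs 0.40 | 6.1% | 6.5% | 8.9% |
| 0.30 vs 0.50 | 7.7% | 11.2% | 20.8% |

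**MAOA, equal sexes, N = 150**

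- Men 0/1 and women 0/1/2, allele frequency 0.4: B = 0.4²/4 = 0.04, W = (0.24+0.48)/2 = 0.36, c_g = √(0.04/0.40) = 0.316. Then r = 0.047 and 0.077, and the rates are 8.8% and 15.4%. Simulation at frequency 0.35 gives 7.7% and 13.3%.
- Men 0/2, simulated at frequency 0.35: 4.8-5.1%, so no inflation.

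**After adjustment.** With the relevant factor in the model, the simulated rate was 4.4-5.5% in every scenario. Where allele frequency was equal across groups, or d was zero, the unadjusted rate also stayed near nominal (4.4-5.8%).

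**The case against.** The strongest reply is that the plan leaves the analysis open rather than choosing a bad one. A reader might infer that it commits to a raw correlation and rules out adjustment. The text does not go that far: it names no coefficient and excludes nothing. What stands is that the only method stated is a correlation, and that following it as written leaves a non-randomised comparison unadjusted.

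Three other tempting readings also go too far:

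- **A fixed 2:1 ND mix.** Both the 100 and the 150 are upper limits, so the achieved ratio is unknown.
- **ND mix as a major confounder.** The background's argument is about response to drug and non-drug cues, while the Aim 3 outcome is ability to regulate activation. A difference in one does not establish a difference in the other. The documents give no allele difference by ND status, and with modest differences the inflation is slight.
- **MAOA level as a measure of sex.** This holds only under the 0/1 versus 0/1/2 coding. The plan states no coding, and MAOA is an example under Genetic measures that does not appear in the analysis sentence.

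The size is also open to challenge. The 12-24% range needs a wide allele-frequency gap and an activation gap, neither of which is in the documents. Saliva is optional, and participants divide between fMRI and EEG and may do only some of the tasks, so the usable number is probably below 150. These points limit how large the problem may be, but do not remove it.

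**Conclusion.** The concern holds in limited form. Aim 3 specifies no covariate and no genotype coding, and its unadjusted correlation can produce an apparent gene effect from population structure.

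Ancestry is the main route. Its effect ranges from negligible (about 6-7% per gene against a nominal 5%) to material (12-24%), under the assumptions listed and at the maximum of 150. A mixed-ancestry sample is itself an inference from open recruitment; the documents do not describe the ancestry of participants. Inflation needs both an allele-frequency difference and an outcome difference across the same factor, and the documents quantify neither. ND mix is secondary, and MAOA is conditional on coding.

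A reader might go further and infer that any positive gene finding here would be false. The documents do not support that: the point is that the stated analysis could not tell the explanations apart. Aim 3 is one of four aims and drives no treatment decision, so this is a cheap improvement rather than a fault that threatens the study.

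**What to change.** Before the genetic data are analysed, amend the Aim 3 paragraph as follows:

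- Replace the correlation with a regression of regulation score on genotype, with terms for self-reported ancestry, sex, ND status and randomised feedback group. Feedback group should be independent of genotype in expectation. It is included for precision, and because the aim concerns activation through neurofeedback, which Noise Control participants do not truly receive.
- State the coding of every marker. Analyse MAOA separately by sex, or code men 0/2 and keep the sex term.
- Report the gene estimate with its confidence interval within the ND and non-ND strata. A rule that asks only for the same sign in both would be weak: with no effect in a stratum, the sign matches half the time by chance.
- Record self-reported ancestry if the Personal History Form or another instrument does not already do so.

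The cost is a change of wording, a few degrees of freedom and at most one questionnaire item. No visit or procedure changes. Self-reported ancestry controls population structure only partly, so some residual confounding should be acknowledged in the report.

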Reward Activation Task (ReAcT): Participants may be randomly assigned to one of two groups. One group, the Veridical Feedback Group, will receive veridical neurofeedback from a reward related region, which may include the VTA, striatum, PFC, etc., while they are inside the MRI or while wearing the EEG headset. The other group, the Noise Control Group, will receive noise feedback that they are instructed is real or yoked sham feedback that is yoked to a participant's feedback in the Veridical Feedback Group. This group will serve as a critical control condition for the experiment. All participants will be debriefed in full about the study groups, random assignment, and the purpose of each group in contributing to our understanding of the reward-related brain regions' role in reward processing in individuals with and without ND.

Participants may complete the ReAcT. The ReAcT consists of two types of runs: test runs (one pre-test and one post-test) and training runs (see Fig. 1 for a sample task design). For both groups the pre-test measures baseline reward-related brain activation prior to receiving rt-fMRI or EEG neurofeedback. For

the Veridical Feedback Group, the training runs train participants to use rt-fMRI or EEG neurofeedback to more efficiently and successfully increase their brain activity. For the Noise Control Group, the training runs serve as a control wherein they continue to try to increase brain activity. For all participants, the post-test measures if participants are better able to activate the brain after training.

Test runs: For both Groups the pre and post-test runs are identical and contain two or three trial types: Activate, Count, and Rest. During Activate trials participants will try to increase reward feelings to personalized images of rewarding items (e.g., favorite food, picture of a pet; see Fig. 1). During Count trials participants will count backwards, providing a standardized period for all participants. During Rest trials, participants are instructed to either not think of anything in particular or to view and think about an image shown to them (neutral-positive image). The test runs will have 5-7 repetitions of each trial, separated by a jittered inter-trial-interval (ITI).

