Training runs: For both Groups training runs will consist of two or three trial types: Activate, Count, and Rest. Participants will be given the same instructions as the test runs. The Activate and Rest trials will now have an interactive display, e.g., a thermometer, graph, signal bar, etc. Feedback display: For the Veridical Feedback Group, during the Activate trials the feedback display will show the average of brain activity, represented as percent signal change from baseline. The feedback display will be updated approximately every 1-10 seconds. For the Noise Control Group the feedback display will either display random values centered at 0 or yoked feedback from a participant in the Veridical Feedback Group. For both Groups, during the Rest trials, the feedback display will show random values that do not reflect brain activity. The purpose of the rest trial during the training runs will be to serve as a visual control. During Count trials, participants will view a neutral-positive cue or image (e.g., shape or picture). Each trial type will be repeated 5-7 times, separated by a jittered ITI.

Passive Viewing Task: In the passive viewing task participants will view the same images they provide for the ReAcT task. Participants with ND will also view some pictures of personalized smoking cues (e.g., cigarette of their choice). MRI participants who are not ND will not view smoking-related images. Participants will be instructed to relax and passively view the images. They will be asked to rate the images for valence (neutral to positive) and provide intermittent ratings of craving.

Reward Learning Task: In this task, participants will be asked to view various neutral or positive images (symbols/pictures/objects, e.g., white square, yellow circle). Some trials will contain the images only and some will contain the images along with a feedback display. The feedback display may vary somewhat in design and may include feedback designs such as: a thermometer, graph, growing/shrinking balloon, etc. Participants goal will be to learn to interact with the feedback display by regulating their thoughts. As part of this interaction with the feedback display, participants will rate their level of motivation prior to, during, and/or after each feedback trial.

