Scale (20 item), the SHAPS, the DEWL, the BVAQ English Questionnaire (40 item), Personal History Form, CES-D, Difficulties in Emotion Regulation Scale (36 item), the General Self-Efficacy Scale, the Fraser Imagery Questionnaire (10 item), the Spontaneous Use of Imagery Scale (12 item), and the State and/or Trait Anxiety Inventories (20 items each) will index state and trait personality measures. We may additionally collect the following smoking-related measures: the Wisconsin Smoking Withdrawal Scale (28 item), the MNWS (may be administered pre and post neurofeedback session), Contemplation Ladder, the Questionnaire of Smoking Urges58 (may be administered pre and post the neurofeedback session). We estimate that completion of these questionnaires will take approximately 35 minutes.

Self-report: participants will be asked to self-report strategies they used to regulate their brain activation. They may be asked to write them down or record them using software such as Audacity (see Pre-Session Questionnaire, Post-Session Questionnaire, and SB Post Session Questionnaire Final as examples). Participants may also be asked to rate their levels of motivation, arousal, enthusiasm, etc. throughout the experiment via making responses on a button box or response dial.

Smoking biomarker: To verify smoking status for nicotine dependent participants, we will measure expired air CO via a handheld monitor (e.g., Vitalograph). To ensure recency of smoking that is sufficient to produce detectable levels of CO, participants with CO levels below the required cutoff will be permitted to smoke one of their own cigarettes outside the lab prior to providing a second breath sample if they choose to do so.

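### The reward-responsivity part of Aim 4 reuses the ReAcT brain signal that Aim 2 trains and tests, and Aim 4 names no comparison between the feedback groups

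*Combined protocol and SAP*

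**What the plan says.** The document does not number its aims; the numbers here follow the order in Purpose of the Study and in Data Analysis & Statistical Considerations.

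- **Aim 2 (does neurofeedback improve activation?).** The BOLD response is compared across "baseline (passive viewing of reward images), Pre-Test (view personalized and non-personalized non-drug cues prior to neurofeedback") and "Training (view personalized, non-drug cues while receiving neurofeedback), and Post-Test (view personalized and non-personalized non-drug cues following neurofeedback"). The stated purpose is: "In this manner we will characterize and quantify individual's ability to increase brain activity to personalized, non-drug rewarding stimuli".
- **Aim 4.** The objective is "To examine the effects of neurofeedback on clinically relevant outcomes, including reward responsivity and smoking related behaviors". The method begins "To assess this we will examine participants brain activity during the Passive Viewing Task and the ReAcT". It then adds minutes to the first cigarette and the number of cigarettes smoked in the break, and correlates each with the ability to raise activation in the ReAcT.
- **The trained task (Reward Activation Task).** "The ReAcT consists of two types of runs: test runs (one pre-test and one post-test) and training runs". Participants may be randomised to Veridical Feedback or Noise Control.
- **Passive Viewing Task.** Participants see the pictures they supplied for the ReAcT; ND participants also see personal smoking cues. "They will be asked to rate the images for valence (neutral to positive) and provide intermittent ratings of craving". Its position relative to training is not given.
- **Questionnaire measures.** SHAPS and DEWL may be completed at screening and again at the MRI or EEG visit. Only the withdrawal scale (MNWS) and the smoking-urges questionnaire are marked for possible use both before and after the neurofeedback session.

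**The concern.** An outcome offered as evidence of clinical relevance should be able to come out differently from the signal that was trained. For reward responsivity, the plan's first-listed evidence is brain activity, and one of the two sources is the trained task itself. If participants learn to raise the target signal in the ReAcT, Aim 2 reports it. Nothing in the text then prevents the same change from being reported under Aim 4 as a clinically relevant effect, with no evidence that response to non-drug reward changed outside the task.

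The plan also lacks the comparison that would attribute any Aim 4 result to neurofeedback. Its one named test correlates activation ability with smoking behaviour. Activation ability is observed, not randomised, so a person who was always good at it may also differ in smoking for unrelated reasons. The Noise Control Group exists to separate these explanations, but the Aim 4 analysis does not use it.

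**Working it through.** No arithmetic applies: the plan states no effect size, variance, error rate or power figure for either aim. The check sets the measures named for Aim 4 against those of Aim 2 and against the task descriptions.

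| Measure named for Aim 4 | Also in Aim 2? | Who has it | Timing and certainty |
|---|---|---|---|
| ReAcT brain activity | Yes: pre-test, training, post-test | Those who do the ReAcT | Runs defined in the task description |
| Passive Viewing, reward pictures | Yes, as baseline | Those who do the task | No post-training run stated |
| Passive Viewing, smoking cues | No | ND only | No post-training run stated |
| Minutes to first cigarette | No | ND only | After the session; firm in the analysis section, optional in the procedures |
| Cigarettes smoked in the break | No | ND only | As above |

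1. **ReAcT.** The three run types in the task description carry the same names as three of Aim 2's four conditions. Aim 4 names no other run, trial type, cue or region for it. This component is therefore not distinguished from Aim 2.
2. **Passive Viewing.** Aim 2 uses passive viewing of reward images as its baseline. If the task is run only before training, neither its reward-picture part nor its smoking-cue part can show an effect of neurofeedback. Valence ratings taken within that task share the limitation.
3. **Smoking measures.** Both are distinct from Aim 2 and bear on carry-over. The Delay to Smoking Assessment covers ND participants only, depends on time and space, and is worded as something that may be done; Data Analysis says it will be done. These statements need reconciling.
4. **Who is left without a separate outcome.** Design & Procedures plans up to 100 ND and 50 non-ND adults. For the 50, reward responsivity is the only Aim 4 domain: 50 / 150 = one third of planned enrolment.
5. **Group comparison.** The Aim 4 paragraph does not mention Veridical Feedback or Noise Control. The section's general remark that VTA time-series analyses will be within and between subjects does not say which groups are compared, and ND versus non-ND would satisfy it equally well.
6. **Unused measures.** SHAPS (14 items), DEWL (31 items) and the picture valence ratings bear on reward outside the trained task, but none appears in the Aim 4 analysis.

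**The case against.** Four points can be made for the plan.

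- **Aim 4 is wider than reward responsivity.** A reader might infer that Aim 4 merely restates Aim 2 and never tests carry-over. The documents do not support this. The same paragraph adds two smoking-behaviour outcomes absent from Aim 2, and Passive Viewing includes smoking cues that the ReAcT does not train. This stands and limits the point to one part of Aim 4.
- **The ReAcT may be meant as a predictor.** The only specified Aim 4 test uses it that way, and the opening sentence could introduce the whole aim, smoking included. This is a fair reading. But the text lists ReAcT activity as a means of assessing the aim and then says smoking is measured as well, so the outcome reading remains open. One sentence would settle it.
- **Brain response is a reasonable measure of reward responsivity.** The background frames the therapeutic target as the reward response to non-drug cues, and the Stimuli section argues that personal pictures give a more realistic reading of reward sensitivity. This supports using brain response in principle. It does not make the trained task an independent source of it.
- **The questionnaires may not be meant as endpoints.** The visit scales are described as indexing state and trait measures, and their completion is optional. This stands: they can complement a post-training brain measure but may not replace it. A reader might also infer that they are completed before training; the text leaves their timing open.

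**Conclusion.** The point holds for the reward-responsivity part of Aim 4. Of the four measures named (ReAcT activity, Passive Viewing activity, minutes to first cigarette, cigarettes smoked), the first is shared with Aim 2. The second is shared for reward pictures and has no stated post-training position. The remaining two are separate, but are confined to ND participants and optional in the procedures. No Aim 4 outcome is assigned a Veridical Feedback versus Noise Control comparison.

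A reader might go further and conclude that the two aims yield one and the same statistic, so that success in Aim 2 guarantees success in Aim 4. That is not shown. The plan gives no ReAcT contrast for Aim 4, regions appear as examples, and the task has several trial types. The defect is an unspecified outcome that permits double reporting; the documents do not establish identical results, and no bias or error rate can be calculated from them.

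The conclusion assumes that the Data Analysis section is the complete statement of the Aim 4 analysis. It affects what may be claimed as clinically relevant; it does not affect the validity of Aim 2.

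**What to change.** In Data Analysis & Statistical Considerations, for Aim 4:

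1. State that ReAcT activation is the Aim 2 outcome and the Aim 4 predictor, and that a change seen only in the ReAcT will be described as target engagement, not as a clinical outcome.
2. Define reward responsivity by measures outside the trained task: valence ratings of the personal pictures and, where completed, SHAPS and DEWL, all taken after the last ReAcT run at the visit. Use the earlier picture ratings (the Camera Return Visit allows for them) and the screening SHAPS and DEWL as baseline. Include Passive Viewing activity only if that task is run after training.
3. Compare these measures and the smoking outcomes between Veridical Feedback and Noise Control, adjusting for baseline where one exists. Keep the correlations with ReAcT activation as supportive.
4. Make the analysis section and the procedures agree on whether the Delay to Smoking Assessment will be done.

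The cost is mostly wording and fixing when existing instruments are given. A post-training Passive Viewing run may mean moving or adding a scanner run. The claimable result may be less favourable. The scales are optional and partly trait-like, so they may be insensitive to one session. The screening baseline may be up to 60 days old, given the permitted interval to the neurofeedback visit.
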